#### 5.6.3 Documentation of Prior and Concomitant Medication Use

All prior and concomitant medications must be documented in the source documents and applicable eCRFs. Concomitant medications will continue to be assessed and recorded at every study visit from the time of informed consent until study participation is complete.

Data from all participants regarding lipid-modifying medications taken throughout the study will be recorded. The number of participants taking a statin or PCSK9-targeted therapy during the study and the number of participants who discontinue background statin therapy, along with the reasons for discontinuation of background statin therapy, will be recorded in the applicable eCRFs.

A participant's maximally tolerated stable statin dose will be determined by the Investigator using his/her medical judgment and available sources, including the participant's self-reported history of lipid-modifying therapy, for at least 8 weeks prior to Screening (Visit 1), and recorded in the applicable eCRFs.

No more than 10% of participants in this study will be statin intolerant. For any participant not taking statin therapy due to statin intolerance (as defined in Inclusion Criterion 4), including those participants taking bempedoic acid or fibrate monotherapy, written confirmation will be required of both the participant and the Investigator stating that the participant was statin intolerant, aware of the benefit of statins to reduce the risk of a MACE, and aware that many other patients who are unable to tolerate a statin were actually able to tolerate a different statin or dose.

Documentation in the eCRF of the reason why a participant is unable to take HIS is required.

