#### 8.2.5 Events of Special Interest

ESIs will be monitored over time by the independent DSMB on a bi-annual basis (ie, approximately every 6 months), regardless of whether these events were reported as AEs. Any events that qualify as an AE or SAE will be reported accordingly (see Sections 8.2, 8.3, and 8.4).

ESIs will include the following hepatic abnormalities, muscle-related abnormalities, new-onset diabetes mellitus (NODM) and/or hyperglycemia, renal abnormalities, changes to antihypertensive medication(s) due to changes in blood pressure, and ophthalmic events (ie, macular degeneration), described as follows:

- AST or ALT > 3 × ULN;
- Total bilirubin >2 × ULN;

- CK >5 × ULN;
- NODM or worsening of glycemic control;

Note: NODM is defined by 1 or more of the following criteria, based upon information from AE, medication, and laboratory data:

- o AE indicating new type 1 or type 2 diabetes;
- o Initiation of anti-diabetes medication with confirmation of the diagnosis of diabetes by blinded external review by experts in diabetology;
- HbA1c  $\geq$ 6.5% ( $\geq$ 0.065 hemoglobin fraction); and/or
- Two consecutive values of fasting plasma glucose that are  $\ge 126$  mg/dL ( $\ge 7.0$  mmol/L).

Note: Worsening of glycemic control will be defined as an HbA1c increase from Baseline >0.5% (>0.005 hemoglobin fraction) and/or a new concomitant medication or increase in current antidiabetic therapy in a participant with a Baseline HbA1c  $\ge$ 6.5% ( $\ge$ 0.065 hemoglobin fraction).

- A >25% decrease in eGFR from Baseline or an eGFR <30 mL/min/1.73 m², calculated using the Chronic Kidney Disease Epidemiology Collaboration equation, and/or an increase in serum creatinine of ≥0.3 mg/dL (≥26.5 μmol/L) from Baseline;
- Changes to antihypertensive medication(s) due to changes in blood pressure in those participants receiving antihypertensive medication(s) treatment at Baseline; and
- Macular degeneration.

These ESIs will be monitored through review of the AE and laboratory databases.

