2.2 Study Design

2.2.1 Overview

This study is a multisite, placebo-controlled, double-blind, randomized Phase 3 study to evaluate the efficacy, safety, and tolerability of obicetrapib in participants with underlying HeFH and/or a history of ASCVD who are not adequately controlled by their lipid-modifying therapy.

Approximately 2400 eligible participants will be randomized in a 2:1 ratio, respectively, to the following treatment groups:

- Obicetrapib group: one 10 mg obicetrapib tablet once daily; or
- Placebo group: 1 placebo tablet once daily.

Treatment allocation will be stratified based on CV risk (HeFH or non-HeFH) and Baseline statin dose (high-intensity statins [HIS] or non-HIS). At least 70% of the participants enrolled into this study must be taking HISs. Participants with underlying HeFH but without a history of ASCVD will comprise up to a maximum of 20% of the total participants enrolled into the study. Starting on Day 1, each participant will self-administer their assigned study drug once daily until Day 365. During the Treatment Period, participants will return to the study site for efficacy and safety assessments. Blood samples for pharmacokinetic (PK) assessment will be collected at specified visits throughout the study. Participants will return to the site for the End Of Study (EOS) Visit (Visit 8) approximately 35 days after last dose of study drug for safety assessments.

A subset of approximately 200 participants from selected study sites who consent to participate will be enrolled in an ambulatory blood pressure monitoring (ABPM) substudy. These participants will have a 24-hour ABPM assessment conducted at Screening (Visit 1) and Visit 6 (Day 270). In order to participate in the substudy, participants must provide written informed consent in a substudy-specific informed consent form (ICF) and must be able to provide an acceptable 24-hour ABPM data collection at Screening (Visit 1).

The study drug blind will be maintained through the EOS Visit (Visit 8). Participants, the Sponsor, Investigators, and all study site personnel involved in the study, including personnel carrying out study procedures, evaluating participants, entering study data, and/or evaluating study data, will

remain blinded to treatment allocations until all participants have completed the EOS Visit assessments and the database has been locked for analysis.

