3.3.6 Concomitant Medications

The Prior & Concomitant Medications case report form where medication start and stop dates are recorded, will be used to determine whether the medications are prior or concomitant to the study treatment. Concomitant medications are defined as those used on or after the first dose of the study drug. Prior medications are defined as those used prior to and stopped before the first dose of study drug. All prior and concomitant medications will be coded using the current World Health Organization (WHO) Drug Dictionary. Counts and percentages of participants taking prior and concomitant medications will be summarized by anatomical therapeutic chemical (ATC) class and preferred term by treatment group and overall, for the Safety Population.

Concomitant medications will be listed.

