3.5.2 Event of Special Interest

Events of special interest (ESIs) include the following: hepatic abnormalities, muscle-related abnormalities, new-onset diabetes mellitus (NODM) and/or hyperglycemia, renal abnormalities, changes to antihypertensive medication(s) due to changes in blood pressure, and macular degeneration described as follows:

- AST or ALT > 3×ULN;
- Total bilirubin > 2×ULN;
- Creatine kinase (CK) > 5 × ULN;
- NODM or worsening of glycemic control;

Note: NODM is defined by 1 or more of the following criteria, based upon information from AE, medication, and laboratory data:

- AE indicating new type 1 or type 2 diabetes;
- Initiation of anti-diabetes medication with confirmation of the diagnosis of diabetes by blinded external review by experts in diabetology;
- HbA1c ≥6.5% (≥ 0.065 hemoglobin fraction); and/or
- Two consecutive values of fasting plasma glucose that are ≥ 126 mg/dL ($\geq \text{mmol/L}$).

Note: Worsening of glycemic control will be defined as HbA1c increase from Baseline $>0.5\%$ (>0.005 hemoglobin fraction) and/or a new concomitant medication or increase in current antidiabetic therapy in a participant with a Baseline HbA1c $\geq 6.5\%$ (≥ 0.065 hemoglobin fraction)

- A $>25\%$ decrease in eGFR from Baseline or an eGFR $<30\text{mL/min}/1.73\text{ m}^2$, calculated using the Chronic Kidney Disease Epidemiology Collaboration equation, and/or an increase in serum creatinine of ≥ 0.3 mg/dL ($\geq 26.5\text{ }\mu\text{mol/L}$) from Baseline;
- Changes to antihypertensive medication(s) due to changes in blood pressure in those participants receiving antihypertensive medication(s) treatment at Baseline and those participants not receiving antihypertensive medication(s) treatment at Baseline; and
- Macular degeneration.

An overview of ESIs described above will be provided including counts and percentages of participants by treatment group, and a listing of each ESI.

Values and changes from baseline will be summarized for ALT, AST, and total bilirubin by visit and treatment group. The number and percent of participants with abnormal values for ALT, AST, and total bilirubin will be summarized. These summaries of participants with abnormal values will be performed overall; by normal Baseline; and by abnormal Baseline for ALT, AST, and total bilirubin individually. Hy's Law criteria ($>3 \times \text{ULN}$ for either ALT or AST, with accompanying total

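### The medication limb of the ESI for worsening glycaemic control names no drug class for a new medication, so followed literally it would count unrelated drugs and dilute that count

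*SAP*

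**What the plan says.** The ESI has two limbs. The first is laboratory-based: "Worsening of glycemic control will be defined as HbA1c increase from Baseline" of more than 0.5%. The second is medication-based. SAP 3.5.2 words it as "and/or a new concomitant medication or increase in current antidiabetic therapy in a participant with a Baseline HbA1c" of 6.5% or more, and Protocol 8.2.5 uses the same medication wording: "a new concomitant medication or increase in current antidiabetic therapy in a participant with a Baseline HbA1c".

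SAP 3.3.6 gives *concomitant* a defined meaning: "Concomitant medications are defined as those used on or after the first dose of the study drug". That definition has no class restriction. Protocol 5.6.3 adds that "Concomitant medications will continue to be assessed and recorded at every study visit".

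Two neighbouring rules in SAP 3.5.2 do name their class. The new-onset diabetes (NODM) criterion reads "Initiation of anti-diabetes medication with confirmation of the diagnosis of diabetes by blinded external review by experts in diabetology". The antihypertensive ESI is derived from antihypertensive drugs, linked to a hypertension-related adverse event within 30 days.

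The SAP reports ESIs as counts and percentages by treatment group, with a listing. It does not plan a split between the two limbs. SAP 3.5 states that safety endpoints are descriptive, without inference.

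**The concern.** In the medication limb, the word *antidiabetic* attaches to the increase in current therapy and not to the new medication. Read word for word, a new antibiotic or analgesic in a participant with Baseline HbA1c of 6.5% or more is an event of worsening glycaemic control, although nothing glycaemic has happened. The SAP gives no derivation rule for this limb, so two programmers could produce quite different counts from the same data.

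Unrelated medication starts occur in both arms. Counting them raises both percentages and pulls the arms together. Because no test is planned, readers and the DSMB will judge these percentages by eye, so the count needs to mean what its label says. The limb also has a specific job: it picks up participants whose treatment was intensified and whose HbA1c may therefore have risen little.

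**Working it through.** The documents give no expected rate for this ESI, so there is no planned figure to reproduce. The check is of the wording and of what the literal rule would do to a true difference.

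**Inputs from the documents**
- Rule: the two limbs above (SAP 3.5.2, Protocol 8.2.5).
- Period: participants "self-administer their assigned study drug once daily until Day 365" (SAP 2.2.1).
- Size: "Approximately 2400 eligible participants will be randomized in a 2:1 ratio" (SAP 2.2.1), so about 1600 v 800.

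**Inputs not in the documents (assumptions)**
- p: the true risk of worsening in participants with Baseline HbA1c of 6.5% or more. Illustrated with 30% on obicetrapib v 20% on placebo, and with 20% v 15%.
- q: the share of them who start an unrelated new drug, taken as equal in both arms and independent of p. Range 10% to 90%.
- f: the share of all participants with Baseline HbA1c of 6.5% or more. Illustrated at 30%.

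**Formula.** A participant is counted unless there is neither a true worsening nor an unrelated new drug:

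observed risk = 1 − (1 − p)(1 − q)

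Subtracting the arms gives observed difference = (true difference) × (1 − q).

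**Worked case, q = 30%.** Placebo: 1 − 0.80 × 0.70 = 44%. Obicetrapib: 1 − 0.70 × 0.70 = 51%. Difference: 10 × 0.70 = 7 points.

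| q | Placebo | Obicetrapib | Difference (points) | Ratio |
|---|---|---|---|---|
| 0 (antidiabetic drugs only) | 20% | 30% | 10 | 1.50 |
| 10% | 28% | 37% | 9 | 1.32 |
| 30% | 44% | 51% | 7 | 1.16 |
| 50% | 60% | 65% | 5 | 1.08 |
| 70% | 76% | 79% | 3 | 1.04 |
| 90% | 92% | 93% | 1 | 1.01 |

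With true risks of 20% v 15%, the 5-point difference becomes 44.0% v 40.5% (3.5 points) at q = 30% and 60.0% v 57.5% (2.5 points) at q = 50%.

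**On the denominator the SAP uses.** The overview is by treatment group, not by Baseline HbA1c. At f = 30% (480 v 240 participants), this subgroup's contribution to the arm percentages, f × observed risk, is:
- q = 0: 9.0% v 6.0%, a difference of 3.0 points;
- q = 30%: 0.30 × 51% = 15.3% v 0.30 × 44% = 13.2%, a difference of 2.1 points;
- q = 50%: 0.30 × 65% = 19.5% v 0.30 × 60% = 18.0%, a difference of 1.5 points.

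The shrinkage factor is the same, but the row does not approach 100%.

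**The case against.** The strongest reply is that nobody would read the rule so literally. The phrase defines glycaemic control, is joined to antidiabetic therapy and follows an NODM criterion that names anti-diabetes medication. That is a fair reading of intent, and it makes this an ambiguity to close, not a deliberate choice to count antibiotics. It does not remove the ambiguity. The authors named the class in the NODM and antihypertensive rules and omitted it here, using a term that the SAP defines broadly.

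Second, SAP section 7 places detailed programming specifications in a separate document, which might already contain a class filter. Protocol 8.2.5 also says that ESIs are monitored through the adverse event and laboratory databases and does not name the medication data there. So it cannot be asserted that the literal count will be produced or that the DSMB will see it. Neither point supplies the missing class in the definition.

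Third, a reader might infer that the ESI would fire for most participants with diabetes. The documents do not support this. Setting 1 − (1 − p)(1 − q) above 0.5 gives q > 1 − 0.5/(1 − p). For true placebo risks of 15%, 20% or 30%, q must exceed about 41%, 38% or 29%, and q is not given.

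Fourth, a reader might infer that a real glycaemic signal would be hidden. That goes too far:
- SAP 3.4.3 analyses HbA1c, HOMA-IR and glucose at Day 365 by ANCOVA.
- SAP 3.5.2 summarises NODM separately and lists each ESI.
- SAP 3.5.3 summarises laboratory change from Baseline, and HbA1c and fasting glucose are in both chemistry panels (Protocol Appendix B).

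What these routes do not give is a clean count of participants whose antidiabetic treatment was stepped up.

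Finally, it is tempting to express the dilution as lost power. SAP 3.5 rules out inference on safety endpoints, so such a figure would describe a test that is not planned.

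**Conclusion.** The wording defect is real and appears in both documents. Context points to an antidiabetic drug, but followed as written the rule counts any new drug in participants with Baseline HbA1c of 6.5% or more, and nothing in the protocol or SAP corrects it. Within that group, a true between-arm difference in this ESI would shrink by the factor 1 − q. For an assumed 10-point difference, 7 points remain at q = 30% and 5 points at q = 50%. This rests on q being equal in both arms and independent of true worsening; the size of q, the true risks and the size of the subgroup are all assumptions.

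The consequence is limited to one descriptive safety count and the DSMB's view of it. Severity is minor.

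**What to change.** In SAP 3.5.2 and Protocol 8.2.5, replace *concomitant* with *antidiabetic* in the medication limb, so that it covers a new antidiabetic medication or an increase in antidiabetic therapy already being taken. State in the SAP that these are identified by the ATC class for drugs used in diabetes, with a start or change date after the first dose of study drug.

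Showing the HbA1c and medication limbs on separate rows would help a reader but is optional.

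The cost is one phrase in each document and one filter in programming. SAP 3.3.6 already has medications coded and summarised by ATC class, so no new data are needed. The change should be made before unblinding, so that a safety event is not redefined after the results are known.

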bilirubin $>2 \times$ ULN) will also be applied to the data. Any potential Hy's Law cases will be listed separately.

Muscle-related abnormalities will be summarized by treatment group and by Baseline eGFR category.

Values and changes from baseline will be summarized for CK levels by visit and treatment group and visit. In addition, the number and percent of participants with abnormal CK values will be summarized. These summaries of participants with abnormal CK values will be performed overall, by normal Baseline CK, and by abnormal Baseline CK. Values of CK from Baseline to EOT will be summarized by treatment group and by Baseline eGFR category.

Cases of NODM will be recorded and summarized using the appropriate system organ class. These events will be summarized by severity and relationship to study drug for each treatment group. Fasting plasma glucose and HbA1c will be monitored as specified in [Table 1 Schedule of Procedures](#).

Baseline eGFR will be summarized by treatment group for actual value and for Baseline eGFR categories. Shift tables of eGFR category from Baseline to EOT will be provided by treatment group. Shift tables of urine albumin-creatinine ratio and urine protein-creatinine ratio from Baseline to EOT will be provided by treatment group.

Participants will be identified who had a diagnosis of hypertension in their medical history and received antihypertensive medication(s) at Baseline. If participants had an adverse event related to hypertension after Baseline (see [Appendix B](#) for preferred terms) and had any change in antihypertension medication within 30 days of the start date of the adverse event, that change in antihypertension medication will be considered as due to a change in blood pressure.

Participants will be identified who did not have a prior diagnosis of hypertension in their medical history and did not receive antihypertensive medication(s) at Baseline. If participants had an adverse event of hypertension and had initiation of antihypertension medication within 30 days of the start date of the adverse event, that initiation of an antihypertension medication will be considered as due to a change in blood pressure.

The number and percentage of participants receiving/not receiving antihypertensive medication(s) at Baseline with changes to or initiation of new antihypertensive medication(s) due to changes in blood pressure will be summarized by treatment group.

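### The SAP's rules for the antihypertensive-change ESI leave out two groups that its own definition covers, and count a change only when a hypertension AE was recorded

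*SAP*

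**What the plan says.** The protocol (8.2.5, and the analysis in 9.2.2.1) defines this ESI as a blood-pressure-driven change of antihypertensive treatment in anyone taking such treatment at Baseline. Neither section asks for a hypertension history or for an AE. Section 8.2.5 says that ESIs are monitored by the DSMB "regardless of whether these events were reported as AEs".

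The definition in SAP 3.5.2 widens the scope to "those participants receiving antihypertensive medication(s) treatment at Baseline and those participants not receiving antihypertensive medication(s) treatment at Baseline", which is everyone.

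The derivation later in SAP 3.5.2 has two rules:

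- Rule 1: "Participants will be identified who had a diagnosis of hypertension in their medical history and received antihypertensive medication(s) at Baseline". The event counts on two conditions: "If participants had an adverse event related to hypertension after Baseline", with a reference to the Appendix B preferred terms, and the participant "had any change in antihypertension medication within 30 days of the start date of the adverse event".
- Rule 2: "Participants will be identified who did not have a prior diagnosis of hypertension in their medical history and did not receive antihypertensive medication(s) at Baseline". The condition is: "If participants had an adverse event of hypertension and had initiation of antihypertension medication within 30 days" of the AE start. Appendix B is not cited here.

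The closing summary is by Baseline antihypertensive use (receiving or not receiving) and treatment group. It has no split or restriction by history.

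**The concern.** The definition depends on one variable, Baseline medication. The rules depend on two, medication and history, and cover only the combinations where the two agree. A participant who takes one of these drugs for another reason, such as coronary disease, and has no hypertension diagnosis meets the definition but neither rule. The same holds for a participant with diagnosed but untreated hypertension. Such participants belong to the displayed groups but cannot enter the numerator.

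The AE condition is a second restriction. If treatment is intensified for a pressure rise and no hypertension AE is recorded, or the change falls outside the 30 days, the ESI is not counted.

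Blood pressure is a dedicated safety question in this trial, with an ABPM substudy and DSMB review. This ESI is the output meant to show pressure rises that were managed with medication. Office and ambulatory readings taken after treatment is intensified may show less of such a rise, and the SAP specifies no adjustment of those readings for treatment changes.

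**Working it through.** The documents give no rate, power or cell size for this ESI, so there is no planned figure to reproduce. The check is one of logic.

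**Step 1: cells.** Cross hypertension history with Baseline medication, and compare protocol 8.2.5 and 9.2.2.1, the SAP definition and the SAP rules.

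| History | Medication at Baseline | In protocol ESI | In SAP definition | SAP rule |
|---|---|---|---|---|
| Yes | Yes | Yes | Yes | Rule 1 |
| No | Yes | Yes | Yes | None |
| Yes | No | No | Yes | None |
| No | No | No | Yes | Rule 2 |

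Against the SAP's definition, 2 of 4 cells have a rule. Against the protocol's definition, 1 of 2 does.

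**Step 2: AE condition.** Suppose a true blood-pressure-driven change in each cell, with three AE states: AE and change within 30 days; AE but change outside 30 days; no AE.

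- Patterns: 4 cells × 3 states = 12.
- Counted under the current rules: 2 cells × 1 state = 2 of 12.
- Counted if the two missing cells are added and the AE condition is kept: 4 × 1 = 4 of 12.
- Eligible for a count without an AE condition: 12 of 12.

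These are logical patterns, not patients, and say nothing about how often each occurs.

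**Step 3: can the loss be sized?** Let u be the share of true events in the two uncovered cells, and a the share of the remaining events that have a qualifying AE. The captured fraction is c = (1 − u) × a. Both inputs are assumptions; the documents supply neither.

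- u = 0, a = 1.0: c = 1.00.
- u = 0.10, a = 0.7: c = 0.90 × 0.7 = 0.63.
- u = 0.30, a = 0.5: c = 0.70 × 0.5 = 0.35.

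A range of 0.35 to 1.00 supports no single figure. Note that u is a share of events; a share of participants could not be substituted for it.

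**Step 4: effect on the comparison.** Assume true rates of 6% and 4% (illustrative) and equal loss in both arms.

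- c = 1.00: difference 6 − 4 = 2.0 points, ratio 1.5.
- c = 0.63: 3.78% and 2.52%, difference 1.26 points, ratio 1.5.
- c = 0.35: 2.1% and 1.4%, difference 0.7 points, ratio 1.5.

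Equal loss shrinks the absolute difference and leaves the ratio unchanged.

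**Step 5: errors in the other direction.** Rule 1 accepts any change near the AE, including decreases and unrelated changes, and the 30-day window does not say whether it runs before or after the AE start. The flagged set is therefore not a pure subset of true events, and c describes only the loss.

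**The case against.** The strongest reply concerns the AE condition. The statement in protocol 8.2.5 that ESIs do not depend on AE reporting describes DSMB monitoring, and the same section ends by naming the AE and laboratory databases as the sources. A medication change is not a laboratory value, so of those two sources only the AE database could show it. Protocol 8.2 also asks for an AE when an abnormal finding requires an intervention, or when a pre-existing condition worsens. A reader might infer that the SAP flatly contradicts the protocol here; the documents do not support that. A tension does remain. Section 9.2.2.1 sets no AE condition, and 8.2.5.5 treats AE reporting as a question to assess once treatment has been changed, so a change without an AE is foreseen. SAP 3.5.2 itself counts worsening glycemic control from a medication change with no AE required.

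The second reply is that the blood-pressure signal does not hang on this row. Office pressure threshold counts (SAP 3.5.4), ABPM (3.5.7), AE tables (3.5.1), concomitant medication by drug class (3.3.6) and unblinded DSMB review (section 4) are all unaffected. That stands. A reader might infer that a pressure effect would go unseen, or that the table is bound to look reassuring. Neither follows, because the loss is confined to one descriptive output and no unequal loss between arms is shown.

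The third reply is that diagnosed but untreated participants were never in the protocol's ESI. That is correct: for them the fault is an incomplete SAP extension, not a departure from the protocol.

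None of these replies supplies a rule for the two uncovered cells.

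**Conclusion.** The point holds on the text. Two of four history-by-medication cells cannot contribute to an ESI that the SAP defines for everyone. One of them, on medication without a hypertension history, is inside the protocol's own definition. This rests only on reading the definition, the two rules and the summary together.

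The AE-within-30-days condition is a further restriction that the protocol does not place on this ESI. The AE-reporting instructions reduce its effect but do not remove it, so it justifies an added supportive count and not the removal of the AE-linked one.

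The size of the under-count cannot be derived from the documents. The 0.35 to 1.00 range comes from assumed inputs and should not be quoted as an estimate. No direction of bias between arms is shown. No hypothesis test is affected, since SAP 3.5 keeps safety endpoints descriptive.

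**What to change.** In SAP 3.5.2:

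1. Classify participants by Baseline antihypertensive use only (yes or no) and drop the history condition, so that all four cells have a rule.
2. Apply the Appendix B terms to both rules.
3. Keep the AE-linked count as the ESI attributed to blood pressure.
4. Add a supportive count per arm of all post-baseline antihypertensive changes (start, addition, increase, decrease, stop), shown by direction and taken from concomitant-medication data whether or not an AE was reported. Label it as not attributed to blood pressure.

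No new data collection is needed: protocol 5.6.3 records concomitant medication at every visit, and SAP 3.3.6 uses start and stop dates. The cost is SAP wording and some extra programming, including a way to identify antihypertensive drugs and dose changes. The supportive count will include changes made for other reasons, such as cardiac events, and these need not fall equally in the two arms. It should be read beside the AE-linked count, not in place of it.
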